11.4.2 Meals

Water (except water provided with each dosing) will be restricted 1 hour prior to and 1 hour after each study drug administration, but will be allowed ad libitum at all other times. Other fluids may be given as part of meals and snacks but will be restricted at all other times throughout the confinement period.

In Period 1, Day 1, subjects will fast overnight for at least 10 hours prior to study drug administration and will continue to fast for at least 4 hours postdose.

In Period 2, Days 1 to 9 and for the evening dose on Day 10, subjects will fast for at least 2 hours prior to each dose (morning and evening, as appropriate) and will continue the fast for at least 1 hour postdose.

In Period 2, Day 10 morning dose, subjects will fast overnight for at least 10 hours prior to study drug administration and will continue to fast for at least 4 hours postdose.

When confined, standard meals and snacks will be provided at appropriate times, except when they are required to fast. When confined in the CRU, subjects will be required to fast from all food and drink except water between meals and snacks.

Each meal and/or snacks served at the CRU will be standardized and will be similar in caloric content and composition and will be taken at approximately the same time in each period.

11.4.3 Activity

Subjects will remain ambulatory or seated upright for the first 4 hours post morning dose, except when they are seated, supine, or semi-reclined for study procedures. However, should AEs occur at any time, subjects may be placed in an appropriate position or will be permitted to lie down on their right side.

There is no specific restriction of activity after dosing in the evening doses.

Subjects will be instructed to refrain from strenuous physical activity which could cause muscle aches or injury, including contact sports at any time from screening until completion of the study.

Use of any tobacco- and/or nicotine-containing products will be prohibited through EOT or ET.

12 TREATMENTS

12.1 Treatments Administered

LOXO-292 will be supplied as 80 mg capsules.

Repaglinide will be supplied as 0.5 mg tablets.

Glucose will be provided as 4 g chewable tablets.

Treatments are described as follows:

Treatment A (Period 1): 0.5 mg repaglinide (1 x 0.5 mg tablet) at Hour 0 on Day 1.

Treatment B (Period 2): 160 mg LOXO-292 (2 x 80 mg capsules) administered BID, approximately every 12 hours, for 10 consecutive days with the Day 10 morning single dose of 160 mg LOXO-292 (2 x 80 mg capsules) coadministered with 0.5 mg repaglinide (1 x 0.5 mg tablet) (within \pm 1 hour of the dosing time of the Day 1 morning dose of Period 2).

Each dose of LOXO-292 and repaglinide will be administered orally with 240 mL of room temperature water. When LOXO-292 and repaglinide are administered concurrently, 240 mL only of room temperature water will be administered for both drugs.

The dose of repaglinide on Day 1 of Period 1 and the coadministered morning doses of LOXO-292 and repaglinide on Day 10 of Period 2 will be preceded by an overnight fast of at least 10 hours. All other doses will be preceded by a 2-hour fast and followed by a 1 hour postdose fast.

On Day 1 of Period 1, immediately following administration of repaglinide, subjects will be provided with 12 g of glucose (3 x 4 g chewable tablets). On Day 10 of Period 2, immediately following administration of repaglinide and at approximately 1 hour after administration of repaglinide, subjects will be provided with 16 g of glucose (4 x 4 g chewable tablets). An additional 100 mL of room temperature water may be taken if required.

Subjects will be instructed not to crush, split, or chew the LOXO-292 capsules or repaglinide tablets, and will be instructed to chew the glucose tablets.

The pharmacy at the CRU will provide each dose in individual unit dose containers for each subject and for each study period.

The exact clock time of dosing will be recorded.

12.2 Dose Modification

The dose and administration of the study drugs to any subject may not be modified. If necessary a subject must be discontinued for the reasons described in [Section 11.3](#).

12.3 Method of Treatment Assignment

Each subject will be assigned a unique identification number upon screening. Subjects who complete the study screening assessments and meet all the eligibility criteria will be assigned a unique identification number at the time of the first dosing, different from the screening number, and will receive the corresponding product.

Subjects will receive each treatment on one occasion in a fixed sequence. The sequence to be used will be AB.

If replacement subjects are used, the replacement subject number will be 100 more than the original (e.g., Subject No. 101 will replace Subject No. 001).

12.4 Blinding

This is an open-label study.

12.5 Treatment Compliance

A qualified designee will be responsible for monitoring the administration of the timed oral doses of LOXO-292 and repaglinide. A mouth check will be performed by the qualified designee to ensure that the subjects have swallowed the study drug. Once a subject has finished the dosing water, the qualified designee will use a flashlight and a tongue depressor to check the subject's mouth. Subjects' hands will also be verified to ensure that the study drugs were ingested. Consumption of glucose tablets will also be verified.

13 STUDY ASSESSMENTS AND PROCEDURES

The Study Events Flow Chart ([Section 6](#)) summarizes the clinical procedures to be performed at each visit. Individual clinical procedures are described in detail below. Additional evaluations/testing may be deemed necessary by the PI or designee and/or the Sponsor for reasons related to subject safety.

For this study, the blood collections for repaglinide and LOXO-292 are the critical parameters and need to be collected as close to the exact time point as possible. All other procedures should be completed as close to the prescribed/scheduled time as possible, but can be performed prior or after the prescribed/scheduled time.

Any nonscheduled procedures required for urgent evaluation of safety concerns take precedence over all routine scheduled procedures.

13.1 Screening

Within 28 days prior to the first dosing on Day 1 of Period 1, medical history and demographic data, including name, sex, age, race, ethnicity, body weight (kg), height (cm), BMI (kg/m²) and history of tobacco use will be recorded. Each subject will have a physical examination, vital sign measurements (heart rate, blood pressure, temperature, and respiratory rate), 12-lead ECG, and the laboratory tests of serum chemistry, serology, thyroid stimulating hormone, pregnancy (females), FSH (postmenopausal females), hematology, amylase, lipase, hepatic and renal function and additional tests as noted in [Section 13.2.6](#).

13.2 Safety Assessments

13.2.1 Physical Examination

Full and abbreviated physical examination will be performed as outlined in the Study Events Flow Chart ([Section 6](#)).

An abbreviated physical examination will include at the minimum, examination of respiratory, cardiovascular, and gastrointestinal systems, with the option for further examination of additional systems as necessary based on reported symptoms/AEs.

Symptom-driven physical examinations may be performed at other times, if deemed necessary by the PI or designee.

13.2.2 Vital Signs

Single measurements of body temperature, respiratory rate, blood pressure and heart rate, will be measured as outlined in the Study Events Flow Chart ([Section 6](#)). Additional vital signs may be taken at any other times, if deemed necessary.

Blood pressure, heart rate, and respiratory rate measurements will be performed with subjects in a supine position (at least 5 minutes), except when they are supine or semi-reclined because of study procedures and/or AEs (e.g., nausea, dizziness) or if deemed necessary by the PI or designee.

Blood pressure and heart rate will be measured using the same arm for each reading. Vital signs (HR, BP, and RR) will be obtained at Screening, Day -1 (Period 1), predose, at 0.75 hours (\pm 10 minutes), 2 hours (\pm 10 minutes), and 4 hours (\pm 10 minutes) on Days 1 (Periods 1 and 2) and 10 (Period 2), and prior to the morning doses on Days 2 through 9 (Period 2) and at EOT (or ET). Vital sign measurements should be carried out prior to and as close as possible to having blood drawn.

13.2.3 ECG Monitoring

Single 12-lead ECGs will be performed as outlined in the Study Events Flow Chart ([Section 6](#)). Additional ECGs may be taken at any other times, if deemed necessary by the PI or designee.

ECGs will be performed with subjects in a supine position (at least 10 minutes). All ECG tracings will be reviewed by the PI or designee.

ECGs will be measured at Screening, Day -1, predose and 2 hours postdose on Day 1 (Periods 1 and 2) and Day 10 (Period 2), prior to the morning doses on Days 2 through 9 (Period 2) and at EOT (or ET). ECGs will be obtained prior to and as close as possible to the scheduled blood draws if scheduled at the same time.

13.2.4 Body Weight

Body weight (kg) will be reported as outlined in the Study Events Flow Chart ([Section 6](#)).

13.2.5 Glucose Monitoring

13.2.5.1 Blood Glucose

Blood glucose determinations will be performed as outlined in the Study Events Flow Chart ([Section 6](#)).

All measurements will be done with a glucose monitor and will be performed by finger stick.

Subjects who manifest hypoglycemic symptoms such as faintness, sweatiness, tachycardia, and headache, may have their blood glucose monitored by finger stick at any time during the study, at the discretion of the PI. In addition, the PI or designee may administer additional oral glucose, 16 g of glucose (4 x 4 g chewable tablets), if the blood glucose (monitored by finger stick) at any of the specified time points is < 60 mg/dL or at any other time based on evaluation of symptoms. For subjects with blood glucose < 60 mg/dL, intervention measurements outlined in protocol [Section 13.2.5.2](#) will be followed.

13.2.5.2 Rescue Intervention for Hypoglycemia

The following steps may be followed at the discretion of the PI:

The subject should be placed in a semi recumbent position. A conscious subject who is safely able to take food/drink by mouth should ingest 15-20 g of glucose. A glucose measurement should be taken 15 minutes later. If hypoglycemia persists, the treatment should be repeated.

Once the blood glucose concentration exceeds 70 mg/dL, the subject should consume a full meal containing at least 60 g of carbohydrate.

Following administration of food, blood glucose concentrations should be measured every 10-15 minutes for the first hour, every 30 minutes for an additional 2 hours, then hourly until blood glucose concentrations have been demonstrated to be stable within the normal range for at least 3 hours and, if present, symptoms have resolved. Oral supplementation may be attempted up to three times prior to intervention with intravenous (IV) dextrose. If a subject displays any signs/symptoms of instability, in the opinion of the PI, IV dextrose will be used immediately. If oral glucose and IV dextrose cannot be administered in an emergency situation, intramuscular glucagon will be used.

Subjects will be offered placement of an IV catheter in the event that dextrose is required. The IV catheter should be placed on the opposite arm from which the PK blood draws are taken.

If subject remains hypoglycemic and there has been no resolution of any associated symptoms despite the interventions described above, the subject should be rapidly transferred to a location where definitive care (i.e., an Emergency Room or Intensive Care Unit) is available.

13.2.6 Clinical Laboratory Tests

All tests listed below will be performed as outlined in the Study Events Flow Chart ([Section 6](#)). In addition, laboratory safety tests may be performed at various unscheduled time points, if deemed necessary by the PI or designee.

Hematology

- Hemoglobin
- Mean corpuscular hemoglobin concentration
- Mean corpuscular volume
- Hematocrit
- Red blood cell (RBC) count
- RBC distribution width
- Platelet count
- White blood cell/leukocyte (WBC) count
- WBC/leukocyte differential (absolute and percent):
 - Basophils
 - Eosinophils
 - Lymphocytes
 - Monocytes
 - Neutrophils

Coagulation

- Prothrombin Time/International normalized ratio
- Activated partial thromboplastin time

Serum Chemistry*

- Blood Urea Nitrogen
- Bilirubin (total and direct)
- Alkaline phosphatase
- AST
- ALT
- Uric acid
- Albumin
- Total protein
- Iron
- Calcium
- Sodium
- Potassium
- Magnesium
- Chloride
- Glucose (fasting)
- Creatinine**
- Cholesterol
- Triglycerides
- Phosphorus
- Creatine kinase
- Amylase
- Lipase

Urinalysis

- pH
- Color and appearance
- Specific gravity
- Protein***
- Glucose
- Ketones
- Bilirubin
- Blood***
- Nitrite***
- Urobilinogen
- Leukocyte esterase***

Additional Tests

- HIV test****
- HBsAg****
- HCV****
- Urine drug screen
 - Opiates
 - Opioids (methadone, oxycodone, and fentanyl)
 - Amphetamines
 - Barbiturates
 - Benzodiazepines
 - Cocaine metabolite
 - Cannabinoids
 - Phencyclidine
- Urine alcohol screen
- Cotinine
- Serum pregnancy test (for females only)
- FSH (for postmenopausal females only)****
- HbA1c
- Thyroid stimulating hormone****

* Samples for serum chemistry will be obtained following a fast of at least 12 hours at Screening and at Check-in (Day -1); at other scheduled times, serum chemistry tests will be performed after at least an 8 hour fast. However, in case of dropouts or rechecks, subjects may not have fasted for 12 or 8 hours prior to the time that the serum chemistry sample is being taken.

** At Screening and prior to dosing (Day -1 of Period 1), creatinine clearance will be calculated using the Cockcroft-Gault formula.

*** If urinalysis is positive for protein, blood, nitrite and/or leukocyte esterase, a microscopic examination (for red blood cells, white blood cells, bacteria, casts, and epithelial cells) will be performed.

**** Performed at Screening only.

13.2.7 Adverse Events

13.2.7.1 Adverse Event Definition

An AE means any untoward medical occurrence associated with the use of a drug in humans, whether or not considered drug related.

A suspected adverse reaction means any AE for which there is a reasonable possibility that the drug caused the AE. Reasonable possibility means there is evidence to suggest a causal relationship between the drug and the AE.

An AE can therefore be any unfavorable and unintended sign (including an abnormal laboratory finding), symptom, or disease temporally associated with the use of a medicinal (investigational) product, whether or not related to the medicinal (investigational) product.

13.2.7.2 Monitoring

Subjects will be monitored from Screening (signing of informed consent) until EOS (or ET if the subject discontinues and does not complete a follow up call) for adverse reactions to the study drugs and/or study procedures. At the EOT (or ET) visit, subjects will be asked how they are feeling prior to check out from the CRU. During the EOS/follow-up phone call, subjects

will be queried with an open-ended question such as: 'How have you been feeling since your last visit?'

AEs (whether serious or non-serious), including abnormal laboratory test value(s), abnormal vital signs, and ECG abnormalities deemed clinically significant by the PI or designee will be evaluated by the PI or designee and treated and/or followed through EOS (or ET). AEs which are ongoing at the EOT or ET which are assessed as related to study drug by the PI (or designee) will be followed through the EOS. AEs which are ongoing at the EOS which are assessed as related to study drug may be continued to be followed until the symptoms or value(s) return to normal, or acceptable levels, as judged by the PI or designee and confirmed by the Sponsor.

Treatment of SAEs will be performed by a physician, either at the CRU or at a nearby hospital emergency room. Where appropriate, medical test(s) and/or examination(s) will be performed to document resolution of event(s). Outcome may be classified as death related to AE, not recovered or not resolved, recovered or resolved, recovered or resolved with sequelae, recovering or resolving, or unknown.

13.2.7.3 Reporting

AEs and SAEs will be collected beginning at informed consent. AEs will be recorded throughout the study (i.e., from signing of the ICF until EOS or ET if the subject discontinues and does not complete a follow up call), either as subject medical history (if the event is reported as occurring prior to signing of the ICF or if the event occurs prior to study drug administration on Day 1 of Period 1 and is assessed as not related to study procedures by the PI [or designee]) or as AEs (if the event occurs after signing of the ICF but prior to study drug administration on Day 1 of Period 1 and is assessed as related to study procedures by the PI [or designee], or if the event occurs after study drug administration on Day 1 of Period 1 through EOT or ET regardless of relationship to study drug). From EOT through EOS or ET, only AEs assessed as related to study drug are to be reported. All SAEs that develop from the time of ICF signing until EOS (or ET, if subject discontinues from the study and does not complete a follow up call) are to be reported.

Unless a subject withdraws consent or is withdrawn from the study and does not complete the follow up call, all subjects must be followed until EOS. AEs ongoing at the time of the EOS which are assessed as related to study drug by the PI (or designee) may be followed until the symptoms or value(s) return to normal or acceptable levels, as judged by the PI or designee and confirmed by the Sponsor. The PI (or designee) should use appropriate judgment in ordering additional tests as necessary to monitor the resolution of events. The Sponsor may request that additional safety tests be performed

The PI or designee will review each AE and assess its relationship to drug treatment (yes [related] or no [unrelated]). Each sign or symptom reported will be graded on the National Cancer Institute (NCI) Common Terminology Criteria for Adverse Events (CTCAE) version 5.0 toxicity grading scale.

Grade refers to the severity of the AE. The CTCAE displays Grades 1 through 5 with unique clinical descriptions of severity for each AE based on the following general guideline ([NCI CTCAE 27 Nov 2017](#)):

Grade 1	Mild; asymptomatic or mild symptoms; clinical or diagnostic observations only; intervention not indicated.
Grade 2	Moderate; minimal, local or noninvasive intervention indicated; limiting age-appropriate instrumental ADL*.
Grade 3	Severe or medically significant but not immediately life threatening; hospitalization or prolongation of hospitalization indicated; disabling; limiting self-care ADL**.
Grade 4	Life-threatening consequences; urgent intervention indicated.
Grade 5	Death related to AE.

A Semi-colon indicates 'or' within the description of the grade.

Note: Not all grades are appropriate for all AEs. Therefore, some AEs are listed within the CTCAE with fewer than 5 options for grade selection. Grade 5 (death) is not appropriate for some AEs and therefore is not an option.

ADL=Activities of Daily Living

* Instrumental ADL refer to preparing meals, shopping for groceries or clothes, using the telephone, managing money, etc.

** Self care ADL refer to bathing, dressing and undressing, feeding self, using the toilet, taking medications, and not bedridden.

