having blood drawn. BP and HR will be measured using the same arm for each reading. Subjects are to be supine for 5 minutes prior to vital sign assessments.

g: Samples for serum chemistry will be obtained following a fast of at least 12 hours at screening and at Check-in (Day -1, Period 1); at other scheduled times, serum chemistry tests will be performed after at least an 8-hour fast. However, in case of dropouts or rechecks, subjects may not have fasted for 12 or 8 hours prior to the time that the serum chemistry sample is being taken.

h: AEs and SAEs will be recorded beginning at informed consent. All AEs will be recorded throughout the study (i.e., from signing of the ICF until EOS or ET if the subject discontinues from the study and does not complete a follow up call), either as subject medical history (if the event is reported as beginning prior to signing of the ICF or if the event occurs prior to study drug administration on Day 1 of Period 1 and is assessed as not related to study procedures by the PI [or designee]) or as AEs (if the event occurs after signing of the ICF but prior to study drug administration on Day 1 of Period 1 and is assessed as related to study procedures by the PI [or designee], or if the event occurs after study drug administration on Day 1 of Period 1 regardless of relationship to study drug). From EOT or ET through EOS only AEs assessed as related to study drug by the PI (or designee) are to be reported. All SAEs that develop from the time of ICF signing until EOS (or ET if the subject discontinues from the study and does not complete a follow up call) are to be reported.

i: 

j: 

k: 

l: All glucose measurements will be done with a glucose monitor and will be performed by finger stick.

m: Glucose will be administered immediately following repaglinide dosing and at approximately 1 hour postdose (after the PK sample).

n: To be performed at the EOT (Day 11, Period 2), or prior to ET from the study. EOT is defined as when the subject is released from the CRU following completion of all assessments through Day 11 of Period 2. ET is defined as when the subject is released from the CRU if the subject terminates the study early. Vital Sign, ECG, and Safety laboratory results for serum chemistry, hematology, coagulation, and urinalysis are to be available for review by the PI or designee prior to subject release from the CRU at the EOT or ET visit.

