As of August 24 2018, PK data were available from 141 patients (from the global Phase 1/2 study). LOXO-292 is absorbed after oral administration with a median time to maximum concentration (Tmax) of approximately 2 hours. Although the PK sampling of LOXO-292 was not long enough to adequately characterize AUC0-inf, the half-life appears to be 20 hours. Low concentrations of LOXO-292 were recovered as unchanged drug in urine indicating that the kidney contributes to overall clearance.

As of September 14, 2018, Loxo Oncology has initiated 16 single patient protocols, Special Access Scheme, or Temporary Authorization Use cases to provide access to LOXO-292 for patients with clinical need not meeting eligibility criteria for the ongoing global Phase 1/2 study. To date, no TEAEs have been attributed to study drug for these patients.

Preliminary PK data available from ongoing studies (LOXO-RET-18014 and LOXO-RET-18015) being conducted in healthy subjects indicate that LOXO-292 has an estimated terminal $t_{1/2}$ of approximately 24 hours after a single dose.

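### All-cause recording of non-serious AEs stops at EOT, nominally about 12 h (0.5–0.6 half-life) after the last LOXO-292 dose, so the B2 TEAE counts mix two recording rules

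*Protocol*

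**What the plan says.** Protocol 13.2.7.3 has three recording rules.

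- From first dosing, AEs are recorded "through EOT or ET regardless of relationship to study drug".
- After EOT, for non-serious events: "From EOT through EOS or ET, only AEs assessed as related to study drug are to be reported".
- Serious events are exempt from that filter: "All SAEs that develop from the time of ICF signing until EOS" are to be reported. Section 13.2.7.4 confirms that this holds whatever the causality.

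The flow-chart AE footnotes (6.1 m and 6.2 h) state the related-only rule with a different start point: "From EOT or ET through EOS only AEs assessed as related to study drug by the PI (or designee) are to be reported". The synopsis, 10.1.1, footnote 6.2 o and SAP Section 3 describe the EOS call as looking for SAEs and drug-related AEs.

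LOXO-292 is "administered BID, approximately every 12 hours, for 10 consecutive days" (12.1), and 11.4.2 confirms an evening dose on Day 10. EOT is release from the unit on Day 11 (footnote 6.2 n), with no clock time. SAP Tables 7.6 and 7.7 place the EOT vital signs and ECG at Hour 24. On half-life, 8.1.1 gives 20 h in patients and says that in healthy subjects "LOXO-292 has an estimated terminal $t_{1/2}$ of approximately 24 hours after a single dose".

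The EOS call is 7 ± 2 days after EOT and asks an open question about how the subject has felt (13.2.7.2). Relatedness is a yes/no rating by the investigator or designee (13.2.7.3) in an open-label study (12.4).

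**The concern.** Secondary objective 2 is the safety and tolerability of multiple-dose LOXO-292 with and without repaglinide. The change of rule comes early in washout, about half a half-life after the last dose. From then on a causality judgement decides whether a non-serious event exists in the database at all, although 13.2.7.1 defines an AE as "any untoward medical occurrence associated with the use of a drug in humans, whether or not considered drug related". The same change applies to a subject who leaves early, at ET.

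SAP 5 and 7.3 split Treatment B into B1 (LOXO-292 alone, Days 1–9) and B2 (Day 10, with repaglinide). SAP 7.3 assigns TEAEs by onset time and investigator judgement and names no last day for treatment emergence. By onset time, an event after discharge falls to B2, the last treatment given. The B2 and Overall columns can therefore pool all-cause events before EOT with related-only events after it, with nothing to mark the join. B1 is collected all-cause throughout for subjects who complete it. A reader comparing B1 with B2 would not be comparing like with like.

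**Working it through.** The documents state no figure for this window, so there is none to reproduce. The quantities below are derived.

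**1. Gap from last dose to EOT.** The Day 10 evening dose is at about Hour 12 after the morning dose, and the EOT assessments are at Hour 24. The gap is 24 − 12 = 12 h, or 12/24 = 0.5 to 12/20 = 0.6 half-life. This is nominal, because the release time is not fixed.

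**2. Concentration remaining at EOT.** First-order decline gives 2^(−gap / half-life):

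| Gap after last dose | Half-life 20 h | Half-life 24 h |
|---|---|---|
| 12 h (nominal) | 66.0% | 70.7% |
| 18 h | 53.6% | 59.5% |
| 24 h | 43.5% | 50.0% |

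Under this decline, the same percentages give the share of the AUC after the last dose that is still to come.

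**3. Share of total LOXO-292 exposure after EOT.** Assume linear one-compartment kinetics, 20 equal doses 12 h apart, and each dose absorbed by the time EOT is reached. With r = 2^(−12 / half-life), the drug on board 12 h after the last dose, in units of one dose, is r(1 − r^20)/(1 − r).

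- Half-life 24 h: r = 0.707, giving 2.41 doses; 2.41/20 = 12.1% of total AUC.
- Half-life 20 h: r = 0.660, giving 1.94 doses; 1.94/20 = 9.7%.

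So about 88–90% of total exposure is already under all-cause recording.

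**4. What the EOS call covers.** It takes place 5 to 9 days after EOT, which is 12 + 120 = 132 h to 12 + 216 = 228 h after the last dose. At 132 h, 2^(−132/20) = 1.0% to 2^(−132/24) = 2.2% of the concentration remains. Five half-lives, a washout convention assumed here and not found in the documents, are 100–120 h. Even the earliest call is later than that. All-cause recording covers 12/120 = 10% to 12/100 = 12% of such a window.

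**5. Length of all-cause collection by segment.** B2 runs from Day 10 Hour 0 to about Hour 24, so about 24 h. B1 has nine days.

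**6. Direction.** The post-EOT rule removes events and adds none. A TEAE count that includes post-EOT events is therefore at or below the all-cause count. The documents give no expected number of unrelated non-serious events after discharge, so the size cannot be calculated.

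**The case against.** The related-only rule is a deliberate choice that recurs throughout both documents. Serious events, including important medical events, are captured to EOS whatever their cause. Events with a reasonable possibility of causation are kept. Most exposure, including the Day 10 coadministration, falls in confinement under all-cause recording. There are 16 subjects and no concurrent control, and SAP 7 excludes inferential safety statistics. All of this stands and keeps the point small.

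Three stronger readings are tempting, and the documents do not support them.

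- A reader might infer that all AE recording passes through a causality filter after EOT. SAEs do not.
- A reader might infer that most of the trial's LOXO-292 exposure escapes all-cause recording. The 66–71% is the concentration left after the last dose. Against total exposure the share is about 10–12%.
- A reader might infer that the Not Related columns of SAP Table 14.3.1.2 must be empty after EOT apart from SAEs. That table rates LOXO-292 and repaglinide separately, so an event related to one drug only is counted as not related to the other. It also has no post-EOT stratum.

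Nor can one say which way the open-label judgement leans. The assessor knows that every subject has just been dosed, which could favour a rating of related.

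None of this answers the remaining point, which is that one TEAE column combines events collected under two rules although the EOS call already asks an open question.

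**Conclusion.** The concern holds in a limited form. All-cause recording of non-serious AEs ends nominally about 12 h after the last LOXO-292 dose, with 66–71% of the concentration remaining. That falls to 44–50% if release is 24 h after the last dose, so whether most of the post-dose exposure lies ahead at EOT depends on a release time that the protocol does not fix. SAEs remain all-cause to EOS.

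The consequence is that B2 and Overall TEAE counts mix two recording rules and can only understate all-cause incidence. The amount is unknown, and only non-serious events judged unrelated are lost. The result bears on a secondary safety objective. It does not touch the primary repaglinide PK comparison.

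The conclusion assumes first-order decline at the protocol's 20–24 h half-life (preliminary and single-dose in healthy subjects), EOT near the SAP's Hour 24, and, for the exposure share, linear one-compartment kinetics. A related-only rule would be easier to defend after washout; the difficulty is that it starts at 0.5–0.6 half-life. This is a cheap improvement to the plan and not a serious flaw.

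**What to change.** In Protocol 13.2.7.3, record all AEs reported up to and including the EOS call regardless of relationship, and keep causality as a recorded attribute instead of a condition of entry. Align 13.2.7.2, footnotes 6.1 m, 6.2 h and 6.2 o, 10.1.1, the synopsis and SAP Section 3, all of which carry the related-only rule or purpose.

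Reconcile the two descriptions of the post-treatment window. Section 13.2.7.3 starts it at EOT and makes ET a possible end, whereas the footnotes start it at EOT or ET and end it at EOS. For a subject who terminates early these are different windows. SAP 7.3 should also state when the treatment-emergent window closes.

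No visit, procedure or form is added, because the call and its open question already exist. The cost is amendment wording and a few more minor unrelated AEs to enter and code. If the rule is left as it is, the clinical study report should state beside the B2 and Overall counts that non-serious AEs after EOT were collected only when judged related.
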